FORM: IRB Proposal – Secondary Use Submission	
NUMBER	VERSION DATE
HRP-UT903	4/27/2023

Clinicaltrials.gov cover page

Official Title of the study

Evaluation of Driscoll Health Plan's Nurture program on nutrition education and food support for pregnant women

NCT number

To be assigned

Date of the document

January 24th, 2024

Unique Protocol ID:

STUDY00005622 (IRB Review Exempt)

Principal Investigator:

[name]

Associate Professor

Population Health, Dell Medical School, University of Texas at Austin

STUDY INFORMATION

Submit this form when seeking determinations for human subject research using secondary data or biospecimens.

1 Confirmation of Secondary Use of Data or Specimen

Click on the following check box (or double click and type an "X" if using Google Docs).

The data or specimens have been or will be collected for purposes unrelated to the purpose of this study.

If this is not the case, please complete HRP-UT901 IRB Proposal Standard Submission or HRP-UT902 IRB Proposal Exempt Submission form.

2 Study Information

Describe the purpose of the research, study background, and hypotheses.

To input text click in the light grey area below.

Purpose:

To assess the impact of Driscoll Health Plan's Nurture program on pregnancy outcomes among participating members.

Background:

Driscoll Health Plan (DHP) is a non-profit, community-based health insurance plan that provides coverage to South Texas and the Rio Grande Valley communities. Their insurance products include STAR Medicaid, STAR Kids, CHIP, and CHIP Perinatal. Affiliated with Driscoll Children's Hospital, DHP offers healthcare services at specialty centers and clinics in various locations, including McAllen, Harlingen, Brownsville, Laredo, Rio Grande City, Eagle Pass, Edinburg, Victoria, and Weslaco.

Maternal health has gained increasing attention. Senate Bill (S.B.) 750, 86th Legislature, Regular Session, 2019, Section 3, for example, mandates the Texas Health and Human Services Commission (HHSC) to develop or enhance statewide initiatives for improving the quality of maternal health care services (Kolkhorst, 2019). It specifies initiatives that contracted managed care organizations (MCOs) must implement and requires progress reporting to the legislature. MCOs are also encouraged to incorporate their own initiatives to enhance maternal healthcare services.

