We will evaluate the impact of DHP's quality improvement pilot program (called, *Nurture*), which included nutrition education and food support offered to a subset of pregnant women aged 30 years and above and were covered by the Medicaid Managed

Care Organization (MCO) plan in their “STAR” and “CHIP” programs during October 2022 and July 2023.

From this population, DHP randomly selected a subset of approximately 500 women during that period, from which approximately 200 were in the program, the “exposed group.” The women who were covered during the same period but were not selected were not exposed to the program and will compose the “comparison group.”

The objective is to compare maternal and neonatal outcomes between those who participated in the program (exposed group) and those who did not (comparison group).

Analysis Plan:

Claims data will be pulled retrospectively from the insurer's database and other administrative sources. Information will include healthcare utilization, maternal outcomes during pregnancy, and neonatal outcomes at and post-delivery. The primary analysis involves comparing the outcomes of the exposed group with the comparison group. Statistical methods appropriate for this type of administrative data will be employed to assess the differences between the two groups, adjusting for potential confounders.

The *Nurture* program’s impact will be evaluated using claims data received from DHP concerning two composite outcomes: adverse maternal health outcomes (Composite 1) and adverse neonatal outcomes (Composite 2), as shown in Table 1 below. In addition, we will explore single outcomes, such as delivery mode (vaginal vs c-section), cost data, and birthweight, adding nuance to our understanding of the program's impact.

We will primarily use logistic regressions to predict the primary, binary composite outcomes for mothers and newborns, adjusted for risk factors such as maternal age, gestational age at the time of enrollment, pre-existing diabetes, hypertension, and being overweight pre-pregnancy (shown in Table 2). The program “dose” variables are anticipated to be continuous predictors that include both ‘usual care’ (i.e., prenatal care visits) and *Nurture* program elements (the dollar value of the gift cards spent up to 30 days after stopping the program, total number of nutrition consult minutes); see Table 3.

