detect rates of 20% or lower among exposed subjects (yellow highlight). If the rate is closer to 35% among comparison subjects, we have enough power to detect rates of 25% or lower among exposed subjects (blue highlight).

Table 4. Statistical power at alpha = 0.05 to detect the program effects of interest assuming two different base rates among comparison subjects.

		% rate among exposed			
		25%	23%	20%	18%
% rate among comparison subjects	35%	78	90	98	99
	30%	28	46	80	93

17 Confidentiality and Data Security Plan

Describe how you will protect confidentiality of the subjects and the security of the data or specimens. Describe where you will store the data or specimens, who will have access to data or specimens; and the data and specimen retention and destruction timelines.

To input text click in the light grey area below.

DHP's data analysis team will anonymize and remove all PHI from all data sets prior to sharing in a way so that no information can be linked back to the individuals.

Data for analysis will be saved as Excel files and, subsequently, in formats specific for analyses using specialized statistical software, in a UT Box folder accessible only to team members involved in the data analysis, such as the PI and the biostatistician.

Data sets will be destroyed (permanently deleted) 3 years after all analyses are completed.

WAIVER OF INFORMED CONSENT

Complete this section if you are seeking a waiver of informed consent for the collection of identifiable data or biospecimens.

To approve a waiver or alteration of informed consent all of the following criteria below must be justified by the researcher.

Only complete the sections below if requesting a waiver of informed consent for the use of readily identifiable data or specimens and the data use is not regulated by HIPAA.

If research solely involves HIPAA protected data, skip this section and complete the Waiver of HIPAA Authorization section below.

18 The research involves no more than minimal risk to the subjects.

To input text click in the light grey area below. Provide protocol specific rationale as to how this study meets this requirement.

19 The waiver or alteration will not adversely affect the rights and welfare of the subjects.

To input text click in the light grey area below. Provide protocol specific rationale as to how this study meets this requirement.

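### Two primary composites serve one purpose with an undivided alpha of 0.05 and no success rule, so the chance of a false programme effect in either direction is about 9 to 10% rather than 5%

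*Combined protocol and SAP*

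**What the plan says.** Section 2 states a single purpose: to assess the impact of the Nurture "program on pregnancy outcomes among participating members". The Analysis Plan in Section 3 then names two primary outcomes, a maternal and a neonatal composite: "We will primarily use logistic regressions to predict the primary, binary composite outcomes for mothers and newborns". Table 1 labels only the remaining outcomes exploratory.

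The contrast is given as follows: "The primary analysis involves comparing the outcomes of the exposed group with the comparison group". On method, the plan adds: "Statistical methods appropriate for this type of administrative data will be employed to assess the differences between the two groups". It gives no test level, sidedness, order of testing, adjustment or success rule.

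The same section puts programme dose variables into the models. The text names two (gift-card dollars spent and consultation minutes). Table 3 lists three under programme uptake, adding packages received. The predictor set is to be identical for every outcome.

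An alpha appears only in Section 16, where Table 4 is headed "Statistical power at alpha = 0.05 to detect the program effects of interest". It is worked for one unnamed composite rate and is not divided between the two.

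**The concern.** With one purpose and two primary outcomes, a significant result on either composite could be reported as a programme effect. The 5% used for planning would then apply to each test and not to the study's conclusion.

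The dose variables widen the gap. Nothing says which coefficient carries the programme claim, so the exposed-versus-comparison contrast, gift-card dollars, consultation minutes or packages received could each be put forward once results are known. The data are retrospective claims, so a rule fixed in writing before analysis is the main protection against choosing among them afterwards.

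**Working it through.** **Inputs.** Two primary composites (Section 3). Alpha 0.05 (Section 16). Exposed 224 and comparison about 1200 (Section 15; Section 3 gives about 200 exposed). Rates as in Table 4. Assumptions, because the plan is silent: two-sided tests, each composite tested at 0.05, and either one sufficient for a claim. The correlation between the two tests is not given, so a range is shown.

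**1. The plan's own figure.** Table 4 was recomputed as a two-sided, unadjusted two-proportion test with a pooled null standard error:

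power = Φ[(d − z·SE0)/SE1], with SE0 = √(p̄(1−p̄)(1/224 + 1/1200)) and SE1 = √(p1(1−p1)/224 + p2(1−p2)/1200).

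For 30% v 20%: p̄ = (44.8 + 360)/1424 = 0.2843, SE0 = 0.0328, SE1 = 0.0298. At z = 1.960 power is Φ(1.196) = 88.4%. At z = 2.241 (alpha 0.025) it is Φ(0.886) = 81.2%.

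| Comparison v exposed | Table 4 | Recomputed, 0.05 | Recomputed, 0.025 |
|---|---|---|---|
| 35% v 25% | 78 | 84.6 | 76.4 |
| 35% v 23% | 90 | 95.4 | 91.6 |
| 35% v 20% | 98 | 99.7 | 99.3 |
| 35% v 18% | 99 | 100.0 | 99.9 |
| 30% v 25% | 28 | 32.0 | 22.4 |
| 30% v 23% | 46 | 56.8 | 44.9 |
| 30% v 20% | 80 | 88.4 | 81.2 |
| 30% v 18% | 93 | 97.3 | 94.7 |

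Only two of the eight printed cells lie within 2 points of the 0.05 column. One-sided versions fit worse, so two-sided is the nearer reading. The mismatch does not touch the error-rate arithmetic. It does mean that the cost of a correction must be measured against the recomputed 0.05 column and not against the printed cells. With 200 exposed, power falls from 85.0% to 76.6% (30% v 20%) and from 80.9% to 71.6% (35% v 25%).

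**2. Error over several tests.** For k independent two-sided tests at 0.05, any false positive has probability 1 − 0.95^k. A false positive in the benefit direction has probability 1 − 0.975^k.

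| What is read as a programme effect | k | Either direction | Benefit only |
|---|---|---|---|
| One contrast per composite | 2 | 9.75% | 4.9% |
| Two dose terms in the text × two composites | 4 | 18.5% | 9.6% |
| Three uptake terms in Table 3 × two composites | 6 | 26.5% | 14.1% |

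**3. Correlation between the two composites** (bivariate normal, k = 2):

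| Correlation | Either direction | Benefit only |
|---|---|---|
| 0 | 9.75% | 4.9% |
| 0.3 | 9.5% | 4.8% |
| 0.5 | 9.1% | 4.5% |
| 0.9 | 7.0% | 3.5% |

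The error exceeds the single-test level (5% either direction, 2.5% benefit) at every value tried.

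**4. After correction.** With both composites tested at 0.025 the either-direction error is 1 − 0.975² = 4.9% if independent. Holm keeps it at or below 5% whatever the correlation.

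**The case against.** The strongest case against the point is that its premises are partly inferred. The Analysis Plan states no test level; 0.05 comes from the power section. No rule says that either composite suffices. Maternal and neonatal outcomes can be read as two questions, each answered separately, and whether separate questions in an observational evaluation need joint error control is disputed. This stands as a limit on certainty, and the figures are conditional on that reading. But both composites are called primary under one purpose, and the plan does not say that they are separate questions. Its silence leaves the stronger claim open.

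A reader might infer that the chance of falsely concluding that Nurture *improves* outcomes is about 10%, or 19% with the dose terms. The documents do not support that. Under two-sided testing half of each test's error lies in the harm direction, so the benefit-only figures are about 4.9% and 9.6%. Reaching 10% for benefit would need one-sided 0.05, which Table 4 does not fit. Nor is 19% a ceiling: Table 3's third uptake term takes the either-direction figure to 26.5%.

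The dose-term figures are also the less certain part. The plan names exposed versus comparison as primary, so reading each coefficient as a programme effect is something it leaves possible, not something it prescribes.

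Finally, the exposed women are those who were reached and opted in, 224 of 511 selected. Selection of that kind can bias both tests, and no multiplicity rule corrects it. That is true, and it is a separate matter.

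**Conclusion.** The point holds in a limited form. The plan has two primary composites, one purpose, one undivided alpha and no success rule. If each composite is tested two-sided at 0.05 and either can support a claim, the error in either direction is 9.75% under independence, 9.1% at a correlation of 0.5 and 7.0% at 0.9. In the benefit direction it is about 4.9%, still twice the level of a single test. The 18.5% and 26.5% figures apply only if every dose coefficient is also read as a programme effect, and they assume independence.

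All of these describe chance error alone. The plan does not say how its conclusion will be used, so no particular consequence for the benefit can be read from it. The gap is worth closing before outcomes are analysed.

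**What to change.** Add to the Analysis Plan, in substance: the single programme test for each composite is the two-sided exposed-versus-comparison contrast already named as the primary analysis; the two p-values are assessed by Holm (the smaller against 0.025 and, if that is met, the other against 0.05); dose and uptake terms and all other outcomes are exploratory, reported with intervals and no significance claim.

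One consequence should be spelled out. Women in the comparison group did not receive the programme, so a group indicator adjusted for uptake is no longer the overall contrast. The uptake terms therefore belong in separate exploratory models, which changes the present rule that every model carries the same predictors.

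Add a 0.025 version of Table 4 (224 v 1200, two-sided, pooled, unadjusted), for exposed rates of 25, 23, 20 and 18%:

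- 35% row: 76, 92, 99, >99
- 30% row: 22, 45, 81, 95

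**Cost.** No new data: a short addition to the text and one more table. At the strictest Holm step, 30% v 20% loses 7.2 points (88.4 − 81.2) and stays above the 80% target. 35% v 25% loses 8.2 points (84.6 − 76.4) and falls below it. With about 200 exposed, both cells miss the target, at 77% and 72%. Once one composite succeeds, the other is tested at the full 0.05. Covariate adjustment is not reflected in these figures.

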In response, DHP, with input from our Factor Health lab at Dell Medical School, introduced the Nurture program for its members as a quality improvement initiative, designed to expand members' access to nutrition education and food purchase support to improve health and pregnancy outcomes.

DHP's Nurture Program:

The *Nurture* program focused on promoting healthy eating through nutrition education and food purchasing support with monthly gift cards for a main local grocery store at the Corpus Christi area. Specifically, the program includes the following components:

- 1. Nurture Monthly Packages:** Sent every four weeks until the member reaches the end of pregnancy (delivery or other reasons, e.g., miscarriage), with a maximum of eight packages. Each package includes:
 - A US\$40 gift card (2 x \$20 each) to a grocery store.
 - A healthy eating information sheet selected from Brighter Bites project (<https://brighterbites.org/>).
 - A set of three recipes.
 - Nutrition-related Frequently Asked Questions (included in four out of the eight packages).
- 2. Two 30-Minute Nutritional Consultations over the phone:** Designed by a Registered Dietitian Nutritionist (RDN) who trained a bilingual nutrition specialist to deliver the consultations. Topics revolved around healthy eating during pregnancy, such as food choices, portion sizes, budget-friendly shopping, food safety, and food preparation. No nutrition therapy advice to manage diseases was provided.

Members had the flexibility to opt out of the program at any time and discontinue receiving packages. Consultations were optional. If they opted out, they continued to receive the DHP benefits as part of their regular coverage.

Secondary Data Analysis Proposal: With funding from the Episcopal Health Foundation, we will conduct a secondary data analysis to evaluate the DHP's Nurture program using their existing administrative data from claims.

Kolkhorst (2019). *Relating to maternal and newborn health care and the quality of services provided to women in this state under certain health care programs.* (S.B. 750). 86th Legislature, Regular Session.
<https://capitol.texas.gov/BillLookup/History.aspx?LegSess=86R&Bill=SB750>.

3 Design, Methodology, and Data Analysis

Provide information regarding study design or data collection methodologies. Describe the data analysis plan, including any statistical procedures or power analysis.

To input text, click in the light grey area below.

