Because we expect cost data to be continuously distributed, linear regressions are expected to be more appropriate. The predictors will remain the same in all models irrespective of outcome, including the “dose” variables.

Table 1. Program outcomes from health claims

Composite outcome 1: Adverse health events during pregnancy	Composite outcome 2: Adverse health events at birth and newborn-related	Exploratory outcomes:

 • Gestational Diabetes Mellitus • Excessive weight gain during pregnancy • Pregnancy-associated hypertension 	
 • Pre-term birth (<37 weeks) • Neonatal Intensive Care Unit (NICU) • Small for gestational age • Large for gestational age • Stillbirths 	
 • Emergency Department visits • Cost (outpatient, inpatient, pharmacy, total) • Delivery mode (vaginal, c-section) • Birthweight collected from hospitals

Table 2. Population descriptors and demographics from health claims

Demographics	Health history (dichotomous)

 • Age (years) • Ethnicity • Location (Nueces/Hidalgo) • Gestational age at enrollment • Gestational age at delivery 	
 • Family history of diabetes mellitus • Pre-pregnancy diabetes mellitus • Pre-pregnancy overweight/obesity • History of gestational diabetes • Chronic hypertension

Table 3. “Dose” variables from program implementation tracking and health claims

Nurture Program uptake	Care Received

 Gift card usage (dollar amount) Packages received (counts) Nutritional consults (duration) 	
 Prenatal visits (counts) Referral to Case Management (dichotomous)

DHP’s Nurture enrollment:

1. DHP receives daily new health plan enrollees from the TX State. Their data analytics team identified new pregnant members aged 30 or older in bi-weekly “cycles” and ran an algorithm to randomly select a list of names to be notified and contacted by DHP’s Community Health Workers (CHWs).
2. Notifications: Members on the roster to be called received an SMS text with a URL to an informational page, which was also mailed as a hard copy to the member’s address on file.
3. Welcome calls: DHP’s CHWs called up to 3 times on consecutive days to welcome the women to the *Nurture* program, explain what to expect, confirm address for mailing out the packages, and book two phone nutritional consultations.

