 - Individuals who could not be reached by the CHW did not receive the packages and the consultations but continued to receive their regular benefits as part of their DHP membership.

The end of participation in the program is marked by the termination of pregnancy (in the form of a claim to the health plan that would flag delivery or a miscarriage/abortion/stillbirth). If such a claim does not reach DHP's system in a timely manner, the woman in the *Nurture* program could receive up to 8 mailout packages.

The Texas Health and Human Services Commission (HHSC) reviewed and approved key member-facing materials, such as SMS text and the informational letter, as part of their regular review process of member-facing materials.

Third group: The women who were selected to be offered the program, but DHP staff could not connect during telephonic outreach, compose a third group. Administrative data on this group will enable us to explore how they compare with the other two groups in terms of their population descriptors and demographics shown in Table 2 above. Answering evaluation questions such as how do those who were reached by the CHWs differ from those who weren't, helping to assess reach from an equity perspective.

4 Data or Specimen Information

Provide information about where the data or specimens will come from (e.g., pathology lab, commercial sources) and what type of data or specimens you will obtain.

To input text click in the light grey area below.

DHP data analysis team will leverage internal databases to compile the required administrative data for analyses, which will be shared as Excel spreadsheets via secured File Transfer Protocol (sFTP).

DHP also contracted the Dell Med lab (Factor Health) services for the delivery of the nutritional consultations and to track gift card balances. These data are owned by Driscoll, who will receive the full data set, de-identify and anonymize it, and merge it to the other relevant sets they will generate for analysis.

The staff involved in the delivery of the nutrition consultation service will not be involved in the data analysis in any way.

5 Identifiers

List all identifiers the researcher will obtain even if the researcher plans to make the data or specimens anonymous. Include information that can be linked directly or indirectly to the subject.

To input text click in the light grey area below. List all identifiers collected.

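### The gift-card dose counts spending and packages that fall after the pregnancy outcomes are settled, yet it predicts those outcomes; cutting it at delivery would not be enough

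*Combined protocol and SAP*

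**What the plan says.** All references are to section 3 (Design, Methodology, and Data Analysis) of the combined protocol and SAP unless stated.

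- **Dose window.** The Analysis Plan measures gift-card uptake as "the dollar value of the gift cards spent up to 30 days after stopping the program". The dose variables "are anticipated to be continuous predictors" in the logistic models of the two primary composites.
- **Same predictors throughout.** "The predictors will remain the same in all models irrespective of outcome", and the plan says that this includes the dose variables.
- **Table 3.** It lists gift-card dollars, a count of packages received and consultation duration. None has a cut-off date.
- **When the programme stops.** Under DHP's Nurture enrollment: "The end of participation in the program is marked by the termination of pregnancy", as flagged by a claim. If that claim is slow to arrive, the woman "could receive up to 8 mailout packages".
- **Opt-out.** Section 2: "Members had the flexibility to opt out of the program at any time and discontinue receiving packages".
- **Package schedule.** Section 2: one $40 package every four weeks, at most eight.
- **Outcomes.** Table 1 places Composite 1 (gestational diabetes, excessive weight gain, pregnancy-associated hypertension) during pregnancy. Composite 2 (preterm birth, NICU, small or large for gestational age, stillbirth) is at birth or newborn-related.

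Nothing in the document limits dose to the time before delivery or before the outcome.

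**The concern.** A predictor offered as a possible cause should be complete before the outcome occurs. Here part of it accrues afterwards. Spending after birth cannot change whether a birth was preterm or whether hypertension developed in pregnancy. The outcome can, however, change the spending: a mother with an infant in NICU, or one who has had a loss, may shop differently, and her end-of-pregnancy claim may arrive sooner or later than others do. The dose coefficient could then show a dose-response that the programme did not produce, in the models of both primary composites.

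**Working it through.** The plan gives no figure for spending after delivery, so there is none to reproduce. The check has three steps.

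**1. Does the rule admit dose after the outcome?** It does on either reading of stopping.
- If stopping means the end of pregnancy, the window runs to 30 days after delivery.
- If it means the day the claim reaches DHP, the window runs to the claim delay plus 30 days.
- The window (30 days) is longer than the package interval (4 × 7 = 28 days). A card mailed shortly before delivery can be spent wholly after it and still count. If mailing continues for 28 days or more, at least one further package falls inside the window unless the cap has been reached.
- For Composite 1 the gap is wider, because spending between diagnosis and delivery counts too.

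**2. How much could it be?** From section 2: $40 per package, every 4 weeks, cap 8, so at most 8 × $40 = $320. Assumed: first package at enrolment, delivery at 39 weeks, mailing continues until the claim arrives.

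Packages = min(8, floor((39 + delay − enrolment week)/4) + 1)

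| Enrolment week | Mailed by delivery | Total, 4-week delay | Total, 8-week delay | Mailed after delivery (4 / 8 weeks) |
|---|---|---|---|---|
| 12 | 7 | 8 | 8 | $40 / $40 |
| 20 | 5 | 6 | 7 | $40 / $80 |
| 28 | 3 | 4 | 5 | $40 / $80 |

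A woman enrolled at 8 weeks has reached the cap by 39 weeks, so nothing is added. Cards still unspent at delivery come on top of these amounts. Averaged over women, two sets of assumptions give similar shares of dose dollars mailed after delivery:
- enrolment uniform over 8–32 weeks, delay uniform over 0–4, 0–8 or 0–12 weeks: 9%, 15%, 20%;
- enrolment at 8–28 weeks, delay of 2, 4 or 8 weeks: about 7.5%, 13%, 22%.

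**3. What does it do to the dose coefficient, and would a cut at delivery cure it?** This is a simulation with no programme effect. Inputs: n = 224 exposed (section 15). Assumed: 30% event rate, 40% of events preterm at 30–37 weeks, 60–100% of the mailed value spent before delivery, adjustment for gestational age at enrolment.

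| Setting | Rejection at 5% level |
|---|---|
| Planned dose, no preterm shortening, no difference in post-birth spending by outcome | about 5% |
| Dose cut at delivery, preterm shortening included | about 94–95% (log OR about −0.7 per $40, i.e. OR exp(−0.7) ≈ 0.50) |
| Dose counted to 30 weeks, preterm shortening included | about 4–5% |

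The first row shows that late dollars unrelated to outcome add noise, not a false association. The second shows that delivery is the wrong cut-off: a woman who delivers early has had less time to receive packages, so the outcome sets the dose. The third removes both problems.

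A further simulation with other assumed inputs (12% preterm, 22% other events, all cards spent) pooled all 224 + 1200 = 1424 women. Rejection was about 8–9% with the planned dose, 8–13% with dose cut at delivery and 4–6% with dose counted to 30 weeks. With 300 runs per setting, the standard error near 5% is √(0.05 × 0.95/300) ≈ 1.3 points, so these differences are only roughly determined.

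**The case against.** The strongest reply has four parts.

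- **The stated primary analysis is exposed versus comparison.** Dose variables are only anticipated, and no model within the exposed group is specified. This stands, and it limits the harm: in the pooled setting the distortion is modest. But the models as described carry dose predictors and name no group term, so the dose coefficients are what would be read.
- **Bias needs a difference by outcome.** Nothing in the documents shows that women with an adverse outcome spend less after birth or have slower claims. This stands. A reader might infer that the 30-day window will by itself produce a false dose-response. The documents do not support that: any rate quoted for it depends on a spending difference that has to be assumed.
- **Late mailing is a possibility, not a fact.** This stands. A reader might infer that most packages arrive after birth for late enrollees. With a first package one week after enrolment at 28 weeks, the eighth goes out at 29 + 7 × 4 = 57 weeks. For 5 of 8 packages to follow a 39-week delivery, mailing would have to continue for 57 − 39 = 18 weeks. The plan says only that this could happen. The 30-day window alone is enough for the point.
- **The window may simply capture redemption of the last card.** That is reasonable for describing uptake. It does not justify using the same quantity to predict an earlier event.

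Early opt-outs are a fair exception, since their 30 days may end before delivery. NICU admission can follow birth, so the statement that the outcome is settled by delivery applies to the other Composite 2 components.

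**Conclusion.** The timing error holds on the current text: a stated rule places dose that accrues after the outcome in the planned models of both primary composites. Its size is unknown. Under assumed claim delays of up to 8 weeks it is $0 to $80 mailed per woman, plus unspent earlier cards. It biases the dose coefficient only if post-birth spending or claim delay depends on the outcome; otherwise it adds noise.

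A reader might also infer that cutting dose at delivery solves the problem. It does not for Composite 2, where shorter gestation itself lowers the dose. Cutting at first diagnosis for Composite 1 has the same flaw: cases would accrue dose only to diagnosis, non-cases to delivery. The point should be settled before the dose variables are derived. It does not undermine an exposed-versus-comparison estimate from a model without dose.

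**What to change.** 1. Estimate the primary effect with an exposed-versus-comparison group term and no dose variables in that model.
2. Make dose-response a separate, secondary analysis. Drop the 30-day extension. Count only packages mailed, dollars redeemed and consultation minutes delivered up to a pre-specified gestational age. That age should be the same for all women and earlier than the outcome being modelled, so it may differ between the composites. Include women still pregnant and event-free at that age, and adjust for gestational age at enrolment.
3. Date the end of pregnancy by date of service, not by when the claim reached DHP. Dollars through the 30-day window can still be reported descriptively as uptake.

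Cost: a few sentences in the Analysis Plan and one derivation step. Under section 4, DHP merges the tracked card data with its own before sharing, so it can compute the variable before de-identification and need not release dates. The downside is some loss of information: later doses do not count, and women enrolled or delivering around the cut-off contribute less. Where card balances were read infrequently, packages mailed by the cut-off × $40 can serve as a proxy.
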